2.5.3.7. Quick Inventory of Depressive Symptomatology (QIDS-C16)

The ACNP recommends that outcome measures reflect all major criteria used in the diagnosis of MDD. For that reason the Planning Committee recommended

additional use of the Quick Inventory of Depressive Symptomatology (QIDS-C16), which meets the ACNP criteria (Rush et al., 2003). The HRSD does not measure hypersomnia, weight gain or problems with concentration or decision making.

2.5.3.8. Beck Hopelessness Scale (BHS)

The Beck Hopelessness Scale is a self-report measure consisting of 20 “yes/no” items (Beck et al., 1974). A total severity of hopelessness is calculated from summing the 20 items and guidelines for interpretation for scores are as follows: 0-3 = minimal hopelessness; 4-8 = mild hopelessness; 9-14 = moderate hopelessness; and 15-20 = severe hopelessness. The BHS is given at screening, weekly during acute treatment and taper phases and then monthly during the follow-up phase.

2.5.4. Safety Assessment and Triggers

2.5.4.1. Columbia – Suicide Severity Rating Scale (C-SSRS)

Suicide is a rare event. As such, suicide rates cannot be used as an outcome measure for an rTMS study. Similarly, the study is of too short a duration to expect to find a significant difference in numbers or lethality of suicide attempts between treatment and placebo (sham rTMS) groups. Nonetheless, there are two areas that can be expected to change with successful rTMS treatment: preoccupation with suicidal ideations or plans. Because this study uses both a lead in period prior to treatment and a sham rTMS treatment group, we are able to compare the rate of parasuicidal behavior in these patients, who are at more serious risk of a suicide completion. One of the newer methods of monitoring patients at risk for suicide is the C-SSRS. The C-SSRS assesses suicidal ideation as well suicidal behavior over a specified time period and is frequently employed by the Food and Drug Administration in research to determine if suicidality is an adverse effect. The form is collected at multiple time points in during the course of the study. Initially, it is collected at baseline to serve as a screener for persons reporting suicidal ideation or behaviors in the past six months. It is also completed weekly during acute treatment and then monthly during the follow-up phase to monitor for the presence of suicidal ideation or behaviors. The sensitivity of this instrument will allow us to identify even “minor” suicide “gestures” as well as more serious attempts.

2.5.4.2. *State-Trait Anger Expression Inventory -2 (STAXI-2)*

The STAXI-2 is a 57-item self-report measure of the experience, expression, and control of anger. The measure consists of six scale, five subscales, and Anger Expression Index which provides a measure of total anger expression. The STAXI-2 is frequently included in risk assessments for violence and used as such in the current protocol.

2.5.4.3. *Adverse events (AEs)*

An AE is any untoward medical occurrence in a patient or clinical investigation subject administered a pharmaceutical product and that does not necessarily have a causal relationship with this treatment. AEs will be identified and documented on the AE CRF in appropriate medical terminology. The severity of the AE and the relationship to the study medication will be determined and reported on the CRF (see below). The severity of each AE will be characterized and then classified into one of three clearly defined categories as follows:

- Mild - the AE did interfere in a significant manner with the subject's normal functioning level. It may have been an annoyance.
- Moderate - the AE produced some impairment of functioning, but was not hazardous to health. It was uncomfortable or an embarrassment.
- Severe - the AE produced significant impairment of functioning or incapacitation and was a definite hazard to the subject's health.

These three categories are based on the investigator's clinical judgment, which, in turn, depends on consideration of various factors such as the subject's report and the PI's observations and/or prior experience. The relationship of the AE to the study medication should be specified by the investigator, using the following definitions:

- Not Related: Concomitant illness, accident, or event with no reasonable association with treatment.
- Unlikely: The reaction has little or no temporal sequence from administration of the study drug, and/or a more likely alternative etiology exists.
- Possibly Related: The reaction follows a reasonable temporal sequence from administration of the drug and follows a known response pattern to the

suspected drug; the reaction could have been produced by the study drug or could have been produced by the subject's clinical state or by other modes of therapy administered to the subject.

- Probably Related: The reaction follows a reasonable temporal sequence from administration of study drug; is confirmed by discontinuation of the study drug or by rechallenge; and cannot be reasonably explained by the known characteristics of the subject's clinical state.
- Unknown: Use only if the cause is not possible to determine.

2.5.5. Control Questionnaire

A questionnaire will be used before and after the first treatment session, and at the end of the final study visit to elicit patient perception of whether they were on active or sham rTMS treatment.

2.6 Sample Size Consideration

The primary hypothesis of the study is that in VA patients with TRMD, rTMS will result in a greater remission rate at the end of acute treatment than sham rTMS. The primary outcome measure in this study is success or failure to achieve remission from depression as defined by a score on the Hamilton Rating Scale for Depression (HRSD24) of 10 or less. The primary analysis will be done as an "intent-to-treat" analysis, i.e. patients will be analyzed in the groups to which they were randomized and drop-outs will be considered treatment failures. The primary hypothesis will be addressed using a logistic regression model with PTSD diagnosis, history of substance abuse, and site as covariates. Based on review of the studies reported in the Introduction Section, the Planning Committee felt that a 10% difference between treatments would be of clinical relevance given the severity of the illness. With a sample size of 180 per group, the proposed study will have a power of 81% to detect an absolute difference between groups of 10% in the percentage of those participants who remit (6% sham and 16% rTMS). Thus, a total of 360 patients are required. This goal of 360 patients, larger than any previous study, also provides a measure of protection should some assumptions be wrong.

3.0 STATISTICAL METHODS

3.1 Statistical Handling Policy

3.1.1 Missing Data and Imputations

For subjects who drop out during the treatment phase will be considered as treatment failures for the purpose of the primary analysis and the missing values will not be imputed. Multiple imputation (MI) method may be used for certain secondary analyses. Multiple imputations will be based on Rubin's procedure (Rubin 1987) using SAS PROC MI and PROC MIANALYZE if needed. Sensitivity analysis will be performed to compare the results from the imputed data based on the two methods, and the complete data without imputation.

3.1.2 Analysis Conventions

This section details general policies to be used for the statistical analyses. Departures from these general policies may be given in the specific detailed sections of this statistical analysis plan. When this situation occurs, the rules set forth in the specific section take precedence over the general policies. The following policies will be applied to all data presentations and analyses.

- All statistical tests will use a significance level of $\alpha = 0.05$. Two-tailed tests will be performed for all analyses that use statistical testing.
- All p-values will be rounded to 3 decimal places. All p-values that round to 0.000 will be presented as '<0.001' and p-values that round to 1.000 will be presented as '>0.999'. Any p-value $\leq \alpha$ will be considered statistically significant.
- Summary statistics will consist of the number and percentage of responses in each category for discrete variables, and the mean, median, standard deviation (SD), minimum, and maximum for continuous variables.
- All mean and median values will be formatted to one more decimal place than the measured value. Standard deviation values will be formatted to two more decimal places than the measured value.
- All percentages will be rounded to one decimal place. The number and percentage of responses will be presented in the form XX (XX.X), where the

- percentage is in the parentheses. The decimal of the percentage may be dropped due to space constraints when creating a table.
- For a continuous variable, if it is normally distributed or approximately normally distributed, Student t test and/or the general linear regression will be performed to test the group difference as proposed in the analysis plan, otherwise, Wilcoxon test and/or a quantile regression will be used as an alternative analysis method; for a categorical variable, Pearson χ^2 test and/or a corresponding generalized linear regression will be performed to test the group difference.
 - All listings will be sorted for presentation in order of treatment group, site number, subject number, and date of procedure or event.
 - All analysis and summary tables will have the population sample size for each treatment group in the column heading.
 - Calculating change from baseline to a visit will be done as follows: change = visit –baseline.
 - Baseline is defined as the last data point before the first treatment is administered. If baseline data are not available, screening data will be used.
 - Baseline measurements and other important covariates will be adjusted if they are not balanced between the two treatment groups unless they are specified in the particular analyses.
 - Version 9.4 of SAS® or higher will be the statistical software package used to produce all summaries, listings, statistical analyses, and graphs.
 - Updated version of MedDRA will be used for adverse event and pre-treatment coding.
 - The current version of the World Health Organization (WHO) drug dictionary will be used for the coding of medications.

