3.7.2.3 Beck Scale for Suicide Ideation (BSS)

BSS is described in Section 2.5.3.4. Higher BSS score indicates higher tendency of suicidal ideation, and each item yields a score of 0 to 2. The overall score of the 21 item test ranges from 0 to 38 (last two items not counted). At each time point of the baseline, end of acute treatment, and end of follow-up, mean and standard deviation of each item will be tabulated by treatment group (Table 3.7.14 a-c). BSS

score at the baseline, end of each treatment block, and end of every four week follow-up time will be tested between the two treatment groups using SAS PROC GLM at each visit adjusted for the baseline. A mixed regression model will be used to test the main effects of treatment using SAS PROC MIXED. The model will include visit, treatment and treatment by visit interaction adjusted for the baseline. A means model will be assumed. An unstructured covariance model will be used in the analysis. If the model fails to converge a compound symmetry covariance matrix will be assumed. The restricted maximum likelihood (REML) method will be used to estimate the covariance parameters. If the treatment by visit interaction is not statistically significant then this term will be removed from the final model. The model is described in Section 3.7.1.2.5. The sample sizes, least-squares means, and standard deviations will be presented at each visit by treatment arm for each study visit (Tables 3.7.15a-c). The assumptions relating to the mixed-effects model will be reviewed by examining residual graphs. Scatter plots of residuals will be used to examine deviations from normality and to assess lack-of-fit. The least square means (LS-means) and their standard errors at each visit will be plotted by treatment groups (Figures 3.7.6a-c).

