3.7.2.6 Secondary Endpoint Analysis Results

The secondary endpoints are defined as severity improvements of MADRS, BSS, BDI, VR-36, and Cognitive function from baseline to end of the acute treatment. Given the several simultaneous hypothesis testing, multiplicity adjustment will be applied. The significance level for the secondary endpoint analyses will be 0.01. The analysis results can be extracted from the above analysis at the time point of end of acute treatment as shown in Table 3.7.34a-c.

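### The non-normality rule in SAP 3.1.2 lets the observed distribution replace a planned linear-model test with an unadjusted Wilcoxon test or an unspecified quantile regression

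*SAP*

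**What the plan says.** SAP 3.1.2 sets a general rule for continuous variables: "if it is normally distributed or approximately normally distributed, Student t test and/or the general linear regression will be performed" to test the group difference; "otherwise, Wilcoxon test and/or a quantile regression will be used as an alternative analysis method". The same section says that where a specific section departs from the general policies, "the rules set forth in the specific section take precedence over the general policies".

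For the BSS, 3.7.2.3 plans a comparison "using SAS PROC GLM at each visit adjusted for the baseline" and a baseline-adjusted PROC MIXED model. It also asks for diagnostics: "Scatter plots of residuals will be used to examine deviations from normality and to assess lack-of-fit". It does not say what follows if the diagnostics look bad. The score runs from 0 to 38.

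In 3.7.2.6, "The secondary endpoints are defined as severity improvements of MADRS, BSS, BDI, VR-36, and Cognitive function" from baseline to end of acute treatment. They are tested at 0.01, with results taken from the analyses above at that time point.

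**The concern.** A baseline-adjusted linear model, a Wilcoxon test and a quantile regression answer different questions. The first compares adjusted means, the second compares ranks and the third compares a chosen quantile given covariates. Under 3.1.2 the look of the data decides which question is asked, and nothing in the rule fixes when the switch happens or what it switches to.

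Two losses follow:

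- A Wilcoxon test on the end-of-treatment score ignores baseline, which the BSS section had planned to adjust for.
- A quantile regression depends on its quantile. At the median, a score with a heavy pile at zero may give an estimate of 0 in both arms even when patients with symptoms improve.

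The BSS is one of five secondary outcomes and is bounded at zero. An open choice of method also leaves room to prefer the more favourable result.

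**Working it through.** **The plan's own figure.** The SAP states no power for the BSS or any other score. Its only power figure is 81% for the binary primary endpoint (2.6: 180 per group, 6% v 16%). With a continuity correction of 1/180 = 0.00556:

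- pooled SE = √(2 × 0.11 × 0.89 / 180) = 0.0330
- unpooled SE = √((0.06 × 0.94 + 0.16 × 0.84) / 180) = 0.0326
- power = Φ((0.10 − 0.00556 − 1.96 × 0.0330) / 0.0326) = 82.0%

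This agrees with 81% and is not in question. Everything below concerns the scores only.

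**Inputs from the SAP.** 180 per arm, 1:1 allocation, two-sided tests, alpha 0.01 for secondary endpoints, BSS range 0 to 38.

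**Assumed inputs.** The score is round(8 × (latent − c)), limited to 0-38. The latent values are bivariate normal with baseline-outcome correlation 0.6, and the benefit is 0.35 latent SD. The constant c sets the share of zeros.

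**Cost of dropping baseline.** Power at alpha 0.01 for ANCOVA with robust errors against Wilcoxon on the end score:

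| Zeros under sham | ANCOVA | Wilcoxon | Loss (points) |
|---|---|---|---|
| 17% | 89% | 71% | 18 |
| 29% | 86% | 70% | 16 |
| 33% | 83% | 68% | 15 |
| 52% | 71% | 60% | 11 |
| 64% | 59% | 51% | 8 |

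The rows come from separate runs. Repeat runs of the same setting differed by a few points. Rank-ANCOVA, which keeps baseline, gave 63-90% over 17-64% zeros, against 59-90% for ANCOVA. So the loss comes mainly from dropping baseline and not from using ranks.

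**Is the switch needed?** With no treatment effect (33-79% zeros, 8,000 trials), the baseline-adjusted linear model with robust errors rejected in 0.9-1.1% of trials at alpha 0.01 and 4.7-5.1% at 0.05. Its error rate holds without normality. If the smaller p-value of the adjusted mean test and Wilcoxon were reported, false positives at 0.01 would rise to 1.6-1.7%. That is a worst case, but 3.1.2 does not rule it out.

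**Median regression.** In the same floored model its estimate was about 0 in 85% of trials at 45% zeros, and in all trials at 55% or more.

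A second data model gives a cross-check. It is zero-inflated, with non-zero scores averaging about 8 v 6, at alpha 0.01:

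| Zeros, sham v active | Adjusted mean | Wilcoxon | Median regression |
|---|---|---|---|
| 60% v 75% | 90-91% | 76-79% | 0-1% |
| 55% v 70% | 89-90% | 75-76% | 0% |
| 45% v 60% | 92-95% | 77-80% | 3-27% |
| 35% v 50% | 94-95% | 81-84% | 43-95% |
| 20% v 35% | 97-98% | 90-93% | 87-96% |

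An exact binomial count explains the first row. The chance that more than 90 of 180 score 0 is 0.9959 at 60% and essentially 1 at 75%, so both sample medians are 0 in 99.6% of trials. At 55% v 70% the figure is 90%. The median fits often reached their iteration limit because of the mass at zero, so their p-values are approximate.

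**The case against.** The strongest reply is the precedence clause. Section 3.7.2.3 specifies the BSS analysis and has no non-parametric branch. Where the authors wanted one they wrote it locally, for example for vital signs (3.8.2) and the baseline instruments in 3.9.3.1 to 3.9.3.5. On that reading the GLM simply stands. This keeps some force, but it does not settle the matter. Section 3.7.2.3 asks for a check on normality and gives no consequence, while 3.1.2 supplies one and directs it at the regressions proposed elsewhere in the plan.

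A reader might go further and infer that the plan makes the BSS a 0 v 0 median test that cannot detect a benefit. The document does not support that:

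- It says quantile and never names the median.
- The same sentence offers Wilcoxon, which does detect the effect, with less power.
- No score distribution is given, and with fewer zeros median regression regains its power.
- The alternative replaces only the t test and linear regression; PROC MIXED has no fallback and stands.

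The loss of adjustment is not universal either. The per-visit GLM is stated as baseline-adjusted for the BSS, VR-36 and cognitive tests, but not for HRSD, MADRS or BDI (3.7.1.2.5, 3.7.2.1.1, 3.7.2.2.1). A non-parametric fallback is also conventional; the objection is to one this open.

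**Conclusion.** The point holds in limited form. SAP 3.1.2 contains a data-driven change of hypothesis with its trigger, target, covariates and choice of method all unstated. It plausibly governs the per-visit tests behind the secondary endpoints.

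Where the planned GLM is baseline-adjusted, moving to Wilcoxon on the score costs about 8 to 18 points of power at alpha 0.01. This rests on the assumed floored score, the 0.6 correlation and the 0.35 SD benefit. The SAP does not say whether Wilcoxon would be run on the score or on the change from baseline. A test on change would use some baseline information and was not simulated.

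The failure of median regression is conditional: it needs that quantile to be chosen and about half or more of each arm to score 0. The primary remission analysis (3.7.1.1) is a logistic regression and is not touched. This should be corrected, but it does not threaten the trial's main conclusion.

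**What to change.** In SAP 3.1.2, replace the switch with a fixed rule. Post-baseline continuous scores are analysed by the baseline-adjusted linear or mixed model with robust (empirical) standard errors, regardless of observed normality. For scores with a floor at zero, such as the BSS, name one baseline-adjusted sensitivity analysis in advance, either rank-ANCOVA or proportional odds. Any quantile regression is at most a further sensitivity analysis, with its quantile and covariates stated. State the baseline adjustment also for the per-visit GLMs of HRSD, MADRS and BDI, where it is now missing.

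The cost is SAP wording and an option in the SAS code; no data collection changes. There is one small downside: for very skewed scores the mean is driven by the high scorers, which the rank-based sensitivity analysis covers.

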2.3 Study Design

This study is a phase II, randomized and balanced within each stratum, double-blind, sham-controlled, intent-to-treat, 2-arm, parallel design, multicenter study in the United States. Three hundred and sixty veterans diagnosed with TRMD are targeted to be enrolled at 9 VA Medical Centers over a three year period. Participants are randomized into a double blind clinical trial to left prefrontal rTMS treatment or to sham (control) rTMS treatment (1:1 ratio) for up to 30 treatment sessions. All participants are evaluated on a wide variety of measures including cognitive, neurological and functional parameters. All will meet DSM-IV criteria for Major Depression and all will

have failed at least two prior pharmacological interventions as defined by the Antidepressant Treatment History Form (ATHF) (Sackeim et al. 1990), i.e., they are TRMD patients. Veterans with PTSD or history of substance abuse are not excluded but detailed histories regarding these disorders are obtained. Participants are not required to stop using anti-depressant medication. The primary dependent measure is remission rate of Hamilton Rating Scale for Depression ($HRSD24 \leq 10$), and secondary analyses will be conducted on other depression and neuropsychological indices. Comparisons between the rTMS (active) and the sham groups will be made at the end of the acute treatment phase to test the primary hypothesis. The overview of the experimental design and procedures is presented in Appendix 5.1.

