3.7.1 Primary Efficacy Analysis

3.7.1.1 Primary Endpoint Analysis

The primary endpoint is the proportion of subjects in each treatment group who achieve “remission” from depression at the end of the acute treatment phase (after a maximum of 30 sessions). “remission” is assessed by a HRSD score ≤ 10 at the end of the acute treatment session (after a maximum of 30 sessions). For patients who dropout before completing the acute treatment phase will be considered treatment failures for the primary analysis on remission rates. The primary null hypothesis is that there is no difference between the treatment and sham groups in the proportion of subjects who are remitted during the acute treatment phase. The primary variable is defined in Section 2.4.1.

Logistic regression will be used for the primary endpoint ($Y = 1$ if remitted,

otherwise $Y = 0$) analysis on the ITT population with treatment group as the testing factor (x). The following covariates will be included in the model: PTSD diagnosis (yes/no as assessed by SCID, z_1), History of substance abuse (yes/no as assessed by SCID, z_2), and Site (9 participating sites, z_3). Given the remission probability $p = \Pr(Y = 1 | x, z_1, z_2, z_3)$ the basic model is defined as follows:

$$\log it(p) = \ln\left(\frac{p}{1-p}\right) = \beta_0 + \beta_1 x + \beta_2 z_1 + \beta_3 z_2 + \beta_4 z_3$$

In the event that the logistic regression does not converge when all covariates are included, the model will be refit by dropping the covariates from the model one at a time in the following order until convergence is obtained.

- a. History of substance abuse
- b. PTSD diagnosis
- c. Site

The number and percentage of subjects in remission at the end of the acute treatment will be summarized and compared using Pearson χ^2 test (Table 3.7.1a). Odds ratio and 95% confidence interval (CI) will be presented using SAS PROC GENMOD. If the coefficient for treatment effect is significant (i.e., the confidence interval for the odds ratio does not include 1), then the null hypothesis will be rejected (McCullagh and Nelder, 1989). The significant level for each covariate coefficient in the model will best determined by Wald test (Table 3.7.1b).

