3.7.2.1.1. MADRS Score Overtime

MADRS score at the baseline, end of each treatment block, and end of every four week follow-up time will be tested between the two treatment groups using SAS PROC GLM at each visit (Tables 3.7.9a-c). A mixed regression model will be used to test the main effects of treatment using SAS PROC MIXED. The model will include visit, treatment and treatment by visit interaction adjusted for the baseline. A means model will be assumed. An unstructured covariance model will be used in the analysis. If the model fails to converge a compound symmetry covariance matrix will be

assumed. The restricted maximum likelihood (REML) method will be used to estimate the covariance parameters. If the treatment by visit interaction is not statistically significant then this term will be removed from the final model. The model is described in Section 3.7.1.2.5. The sample sizes, least-squares means, and standard deviations will be presented at each visit by treatment arm for each study visit (Tables 3.7.9a-c). The assumptions relating to the mixed-effects model will be reviewed by examining residual graphs. Scatter plots of residuals will be used to examine deviations from normality and to assess lack-of-fit. The least square means (LS-means) and their standard errors at each visit will be plotted by treatment groups (Figures 3.7.4a-c).

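### Where a section is silent, baseline adjustment waits on observed imbalance: this leaves open baseline HRSD24 in the primary model and the baseline score in five sets of visit tests, including those for MADRS and BDI

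*SAP*

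**What the plan says.** The general rule in SAP section 3.1.2 reads "Baseline measurements and other important covariates will be adjusted if they are not balanced between the two treatment groups". The sentence then exempts covariates that a particular analysis specifies, and the same section lets specific sections override general policies. It does not say how imbalance is judged or which covariates count as important. Sections 3.5.1 and 3.5.2 plan significance tests of baseline balance but do not link them to model choice.

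The specific sections differ in what they fix:

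| Analysis | SAP section | Baseline score in model? |
|---|---|---|
| Primary logistic model | 3.7.1.1 | Not stated |
| Visit GLM: HRSD, MADRS, BDI | 3.7.1.2.5, 3.7.2.1.1, 3.7.2.2.1 | Not stated |
| Visit GLM: QIDS-C16, BHS | 3.7.3.1.1, 3.7.3.2.1 | Not stated |
| Visit GLM: BSS, VR-36 | 3.7.2.3, 3.7.2.4 | Yes |
| Cognitive GLM and mixed models | 3.7.2.5.1 to 3.7.2.5.8 | Yes |
| Mixed models for all the depression, BSS, VR-36 and BHS scores | same sections as their GLMs | Yes |

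The primary section opens its list with "The following covariates will be included in the model: PTSD diagnosis" and goes on to history of substance abuse and site. It also gives an order for dropping these three if the model fails to converge. For MADRS the visit scores "will be tested between the two treatment groups using SAS PROC GLM at each visit (Tables 3.7.9a-c"), with no baseline term. For BSS the wording is "SAS PROC GLM at each visit adjusted for the baseline".

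Section 3.7.2.6 defines the secondary endpoints as improvement from baseline to the end of acute treatment and takes the results from the analyses already described. It does not say whether the GLM or the mixed model supplies them. It adds: "The significance level for the secondary endpoint analyses will be 0.01".

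**The concern.** An analysis plan written before any analysis, as SAP section 1.0 says this one is, should settle which covariates enter each model. A rule that waits for observed imbalance gives that up wherever a section is silent. One analyst could read the primary covariate list as closed. Another could find baseline HRSD24 imbalanced and add it under the general rule. Both could claim to follow the plan, and they would report different primary p-values.

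Baseline HRSD24 is an obvious candidate covariate, because remission means that the same scale has fallen to 10 or less. Section 3.9.2 itself lists baseline severity as a possible prognostic factor.

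For the secondary endpoints, MADRS and BDI may be tested without baseline while BSS, VR-36 and cognition are tested with it, all at 0.01. At stake are precision and a fixed choice of model.

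**Working it through.** **1. The plan's own figure.** Inputs from section 2.6: "With a sample size of 180 per group", 6% v 16%, and a stated power of 81%. Two-sided alpha is 0.05 (section 3.1.2). With pooled rate 0.11:

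- SE under the null = √(2 × 0.11 × 0.89 / 180) = 0.0330.
- SE under the alternative = √((0.06 × 0.94 + 0.16 × 0.84) / 180) = 0.0326.
- Power without continuity correction = Φ((0.10 − 1.96 × 0.0330) / 0.0326) = 86.1%.
- Power with correction 1/180 = Φ((0.10 − 0.0056 − 1.96 × 0.0330) / 0.0326) = 82.0%.

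The corrected formula needs 176 per arm for 81%. The stated figure is therefore reproduced, and nothing below changes it.

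**2. Cost of leaving baseline out of a score test.** The SAP gives no baseline-outcome correlation r, so r = 0.3 to 0.6 is an assumption. Adjusting for baseline multiplies the error variance by 1 − r², so the unadjusted test of the score needs 1/(1 − r²) times as many patients:

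- r = 0.3: 1/0.91 = 1.10, or 10% more.
- r = 0.6: 1/0.64 = 1.56, or 56% more.

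Analysing change from baseline without a baseline term does not remove the loss. With equal variances at both times, the variance of change is 2(1 − r) in units of the score variance. The ratio to the adjusted analysis is 2/(1 + r): 1.54 at r = 0.3 and 1.25 at r = 0.6.

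At the secondary level of 0.01, with 180 per arm and an assumed effect of 0.3 SD, the noncentrality is 0.3 × √90 = 2.846:

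- Unadjusted: Φ(2.846 − 2.576) = 61%.
- Adjusted, r = 0.3: Φ(2.846/√0.91 − 2.576) = 66%.
- Adjusted, r = 0.5: Φ(2.846/√0.75 − 2.576) = 76%.

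**3. The conditional rule itself.** This was simulated with 180 per arm, effect 0.3 SD, alpha 0.05 and 20,000 replicates. The trigger was assumed to be a baseline t-test with p < 0.05, since the SAP states none.

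| r | Power, adjust only if imbalanced | Power, always adjust | Type I error, conditional rule |
|---|---|---|---|
| 0.3 | 81.4% | 84.4% | 4.5% |
| 0.5 | 81.9% | 90.4% | 4.4% |
| 0.7 | 82.7% | 97.7% | 3.6% |

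No adjustment gives about 81% power. Always adjusting has type I error of about 4.8%. The rule thus recovers almost none of the available precision, and its error rate is at or a little below nominal.

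**4. Primary endpoint.** Logistic models were simulated at 6% v 16%, with 4,000 replicates and assumed baseline effects per SD on the log-odds scale:

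| Log-odds per SD | Without baseline | With baseline | Conditional odds ratio |
|---|---|---|---|
| −0.3 | 86.9% | 86.9% | 3.01 |
| −0.6 | 86.4% | 88.0% | 3.10 |
| −1.0 | 87.2% | 89.8% | 3.33 |

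The gains are 0, 1.6 and 2.6 points. A separate simulation that also carried PTSD, substance abuse and eight site terms gave 86.0% to 87.5% at −0.5 and 87.6% to 89.4% at −0.8. The marginal odds ratio is (0.16/0.84)/(0.06/0.94) = 2.98, so the adjusted model estimates a slightly different quantity.

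**5. Events available.** Expected remissions are 180 × 0.06 + 180 × 0.16 = 10.8 + 28.8 = 39.6. The primary model has 1 treatment, 1 PTSD, 1 substance abuse and 8 site terms, or 11 in all. Baseline HRSD24 makes 12.

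**The case against.** The strongest reply is that the general rule has little reach. It yields to any section that specifies covariates. The primary section does so and gives a drop order, and every score mixed model already includes baseline. On that reading the primary model is closed and valid without baseline HRSD24, and adding it is a preference worth at most about 3 points. It would also add a term to a model with about 40 expected events. Much of this stands. It limits the point to what the sections leave unsaid, and it makes the primary-model part a modest improvement. It does not settle which model feeds Table 3.7.34, nor why MADRS and BDI visit tests differ from those for BSS and VR-36.

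Four stronger readings are tempting, and the document does not support them:

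- **That no score model carries the primary covariates.** The cognitive models include substance abuse, though not PTSD or site.
- **That the score models ignore the randomisation strata.** Section 2.3 says only "randomized and balanced within each stratum". The SAP does not name the strata, so any claim about standard errors is conditional on what they are.
- **That several chance imbalances are certain.** The 17 variables listed in section 3.5.1, if independent, give at least one p < 0.05 with probability 1 − 0.95^17 = 58% and 17 × 0.05 = 0.85 on average. Section 3.5.2 adds more tests, so some are likely, but the trigger need not be a p-value at all.
- **That the rule inflates false positives.** The simulation shows 3.6% to 4.5%.

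**Conclusion.** The point holds as a gap in prespecification with a loss of precision. Its larger part concerns MADRS and BDI. If the visit GLM supplies their results, they are tested at 0.01 without baseline, at a cost equivalent to about 10% to 56% more patients for r between 0.3 and 0.6. If the mixed model supplies them, that cost disappears, and what remains is that the plan does not say so. The HRSD, QIDS-C16 and BHS visit tests have the same gap but lie outside the five secondary outcomes.

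For the primary endpoint at 6% v 16%, including baseline HRSD24 adds about 0 to 3 points of power. The main benefit there is that the model can no longer be read two ways. A reader might infer that the trial is underpowered or its primary test invalid; neither follows. The 360 patients and the 81% are unaffected. The sizes rest on assumed correlations, baseline effects and, for the conditional rule, an assumed p < 0.05 trigger.

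**What to change.** - **Section 3.1.2:** delete the imbalance trigger. Balance tests may stay as description if they do not select covariates.
- **Section 3.7.1.1:** add baseline HRSD24 as a continuous covariate and give it a place in the drop order.
- **Sections 3.7.1.2.5, 3.7.2.1.1, 3.7.2.2.1, 3.7.3.1.1 and 3.7.3.2.1:** add the baseline value of the outcome to the post-baseline visit GLMs, matching BSS and VR-36.
- **Section 3.7.2.6:** state that the baseline-adjusted model supplies Table 3.7.34, and name it.
- **Score models:** if PTSD, substance abuse or site are the randomisation strata, carry them into these models too.

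The cost is SAP wording, since the variables are already collected. The downside is one more parameter in a primary model with about 40 expected remissions, and an odds ratio that is conditional on baseline HRSD24 and should be described as such.
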